Test scores were simulated based on means and standard deviations of pretest and posttest scores from a previous study. Pretest scores for both clauses were sampled from a Normal distribution with $M=3.0$ and $SD=2.5$, rounding to the nearest integer, with a minimum score of 0 and maximum score of 7 items correct (corresponding to the >40% correct study eligibility criteria). Posttest scores for untreated clauses were sampled from a Normal distribution with a correlation of .90 with pretest scores and $M=3.0$ and $SD=2.5$, rounding to the nearest integer, with a minimum score of 0. Posttest scores for treated clauses were sampled from a Normal distribution with a correlation of .90 with pretest scores, rounding to the nearest integer, with a minimum score of 0, and $M=5.5$ and $SD=4.0$ for the syntax stories at home condition ($ES=+1.0$), $M=4.0$ and $SD=4.0$ for the parent recasts condition ($ES=+0.4$), $M=6.0$ and $SD=3.5$ for the syntax stories in the lab condition ($ES=+1.2$), and $M=8.0$ and $SD=3.5$ for the lab recasts condition ($ES=+2.0$).

Based on the above effect size estimates, power for detecting main effects in Aim 1 exceeds .95 for the syntax stories at home, syntax stories in the lab, and lab recasts. Power is .61 for detecting main effects of parent recasts (i.e., the effect of parent recasts would need to exceed .50 to be detected with 80% power). Power for treatment effect contrasts is .75 to detect differences in syntax stories at home and parent recasts effects, .90 to detect differences in parent recasts and syntax stories in the lab effects, and .99 to detect differences in parent recasts and lab recasts effects. Other contrasts (e.g., syntax stories at home vs. syntax stories in the lab) have power less than 80% if the expected effect sizes hold true (i.e., +1.0 vs. +1.2); differences in effects would need to exceed 0.35 logits (2 raw score points) in order reach statistical significance with 80% power.

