The influence of dose (Aim 2) was simulated by predicting different dose distributions for each condition. These distributions were simulated and then we randomly sampled from the distribution for each case. Hypothesized distributions of dose lead to substantial changes in the result, and thus we make our method of construction these distributions clear here. We assume that a minimum dose is achieved during the training visits (home condition) or by attending at least 1 session (lab condition) for all children. The two in-lab conditions are highly similar and both assume that 25% of participants attend between 1 and 12 sessions, 25% attend between 12 and 16, and the remainder have perfect attendance. This is a conservative estimate based on attendance data from our summer camp study.

The two at-home conditions require slightly more explanation. We assume for recasts that the first quartile has a dose of up to 1 recast/5 min for 60 min per week. The next quartile extends up to 1 recast/5 min for 120 min per week. The third quartile ranges up to a dose of 1 recast every 3 min for 120 min per week and the last quartile assumes target delivery. Similarly, syntax stories at home escalates from reading 1x/week to reading 2x/week to reading 4x/week (as asked) to reading 1 syntax story daily as the maximum. Several families in the pilot data for the syntax stories read the provided syntax stories daily.

Table 1. Hypothesized dose delivered by condition, in quartiles

	Recasts in lab	Stories in lab	Recasts at home	Stories at home
minimum	60	60	60	60
1st quartile	768	768	96	240
median	912	930	192	460
3rd quartile	960	960	320	960
maximum	1008	960	960	1680

Next the gain obtained from each dose was estimated by multiplying the dose provided by a value drawn from a uniform distribution ranging from .0005 to .006, to account for the fact that some children will be more responsive to any given dose than others. Finally, the gain was added to the pretest scores to yield posttest values. Simulations were checked to ensure that final post-test means and standard deviations for the treated structure were in line with estimates for post-test gains used for Aim 1 simulations. Planned statistical analysis were carried out over the simulated data and these simulations were repeated 1000 times.

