Simulations that include dose indicate power of .93 for models that include dose and time. Effects of treatment, dose, and power combined are not detectable because this estimation of dose confounds the distribution of dose with treatment delivery approach, as we hypothesize in the strategy. It suggests that three-way interactions will only be detectable if the delivery method modifies the benefit obtained from each exposure to the target form.

Power Analysis for Eye Tracking

Power analyses were carried out using G*Power (Faul, Erdfelder, Lang, & Buchner, 2007). Our preliminary data focused on eye-movements during a single test point, thus we do not have relevant estimates of fixation changes at multiple time points or following interventions. Consequently, we based our sample size on power analyses for production ($n=120$) and calculated the smallest changes in Structural Sensitivity that will be detectable with varying levels of power.

In our preliminary data ($n=15$), children with DLD revealed $M = 0.02$ and $SD = 0.17$ in the late window. With the proposed sample size, effect sizes of $d=.30$ will be detectable with 80% power, $d=.34$ with 90% power, and $d=.42$ with 99% power. These correspond to increases in Structural Sensitivity of $M=.05$, $M = .06$, and $M = .07$ respectively. For reference the TD children in our Preliminary Data have a Structural Sensitivity score that is $M=.29$ larger than that of the children with DLD. Based on this benchmark, improvements across time points that are 17-24% in magnitude would be detectable in the current design. This suggests that this study is adequately powered to detect relatively small changes in linguistically mediated fixations.

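### As described, the dose simulation behind the .93 power for Aim 2 does not reproduce the Aim 1 post-test inputs it is said to match, most plainly the lab-recast mean

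*Protocol*

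**What the plan says.** All of this stands in the Protocol, section Power Analysis for Production.

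- **Aim 1 inputs.** Pretest scores are Normal, "with $M=3.0$ and $SD=2.5$, rounding to the nearest integer, with a minimum score of 0 and maximum score of 7 items correct". Treated-clause post-tests correlate .90 with pretest, are rounded and are floored at 0. Their mean/SD are 8.0/3.5 (lab recasts), 6.0/3.5 (lab stories), 4.0/4.0 (home recasts) and 5.5/4.0 (home stories).
- **Dose simulation.** Each child's dose is sampled from the Table 1 distribution for the arm. The gain is that dose times "a value drawn from a uniform distribution ranging from .0005 to .006", and is added to the pretest score. No other source of variation is described.
- **Consistency statement.** "Simulations were checked to ensure that final post-test means and standard deviations for the treated structure were in line with estimates for post-test gains", with Aim 1 named as the source of those estimates.
- **Result.** "Simulations that include dose indicate power of .93 for models that include dose and time".

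The same section warns that the assumed dose distributions change the result substantially, and gives that as the reason for setting out how they were built.

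**The concern.** The consistency statement is the only assurance that the dose simulation and the main production simulation describe the same trial. The .93 is the only power figure for the Aim 2 dose question, whose key test is the dose-by-test-point interaction in the two home arms. If the generator gives less outcome variation than Aim 1 assumes, the dose slope looks easier to detect than it would be under the Aim 1 inputs. If it also misses an arm mean by more than 2 points, the printed description and the reported check cannot both be complete.

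**Working it through.** **Inputs.** Table 1 dose (minimum, first quartile, median, third quartile, maximum):

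- lab recasts 60/768/912/960/1008
- lab stories 60/768/930/960/960
- home recasts 60/96/192/320/960
- home stories 60/240/460/960/1680

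The gain per exposure is Uniform(.0005, .006), with mean (.0005 + .006)/2 = .00325. The pretest is N(3.0, 2.5) rounded and clipped to 0–7, which realises mean 3.08 and SD 2.15. Assumptions: dose is uniform within each quartile band, and dose, gain per exposure and pretest are independent.

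**Means.** Mean dose is the average of the four band midpoints. For lab recasts this is (414 + 840 + 936 + 984)/4 = 793.5, so the mean gain is 793.5 × .00325 = 2.58 and the post-test mean is 3.08 + 2.58 = 5.66.

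**SDs.** Pretest and gain are independent, so post-test SD = √(pretest SD² + gain SD²). For lab recasts this is √(2.15² + 1.55²) = 2.65.

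| Arm | Mean dose | Mean gain | Gain SD | Rebuilt mean/SD | Aim 1 mean/SD |
|---|---|---|---|---|---|
| Lab recasts | 793.5 | 2.58 | 1.55 | 5.7 / 2.65 | 8.0 / 3.5 |
| Lab stories | 792 | 2.57 | 1.54 | 5.7 / 2.64 | 6.0 / 3.5 |
| Home recasts | 279.5 | 0.91 | 0.97 | 4.0 / 2.36 | 4.0 / 4.0 |
| Home stories | 632.5 | 2.06 | 1.96 | 5.1 / 2.91 | 5.5 / 4.0 |

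A simulation of 1,000,000 draws per arm gives the same values.

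**Ceiling on the lab-recast mean.** With every child at the maximum dose, the mean gain is 1008 × .00325 = 3.28. The post-test mean is then 6.28 with a pretest mean of 3.0, 6.36 with the clipped 3.08, and 6.48 if the pretest is truncated to 0–7 instead (mean 3.20). No dose distribution within Table 1's range reaches 8.0.

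**Bounds on the SDs.** An unbounded pretest (SD 2.5) gives 2.94, 2.94, 2.68 and 3.18 in table order, all still short. For home recasts, even perfect correlation between pretest and gain gives only 2.5 + 0.97 = 3.47.

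**Like-for-like SDs.** Two adjustments favour the plan.

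1. Rounding and flooring the Aim 1 post-tests lowers the realised target SDs to 3.48, 3.38, 3.48 and 3.72.
2. Scoring the rebuilt post-test y as 20 binary items adds variance E(y) − E(y²)/20. For home recasts this is 3.99 − (3.99² + 2.36²)/20 = 2.92, so SD = √(2.36² + 2.92) = 2.91. The four SDs become about 3.27, 3.28, 2.91 and 3.44.

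The shortfalls are then about 6%, 3%, 16% and 8%.

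**Change scores.** The Aim 1 inputs for the home arms imply a change SD of √(2.5² + 4.0² − 2 × .90 × 2.5 × 4.0) = √4.25 = 2.06. Home stories (1.96) is close; home recasts (0.97) is under half.

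**Power.** The .93 cannot be uniquely reproduced, because the fitted model and sample are not stated. It was approximated by regression of change scores on dose, home arms only, 30 per arm, with and without a treatment term, on raw and logit scales, for the treated clause and for both clauses pooled.

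| Generator | Dose-by-time power |
|---|---|
| As described | .94 to 1.00 |
| SDs raised toward Aim 1, .90 correlation kept | .89 to above .99 |
| Missing variance added as independent noise | .53 to .85 |

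The closest variant to .93 as described was .944. These are approximations to the mixed logistic model, not a rerun of it.

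**The case against.** The strongest reply is that Aim 2 is tested in the home arms, where the means agree with Aim 1 to within 0.4 points. The section models 20 binary items per test, so item noise may have been present without being restated. With it, and with floored targets, three of the four SDs are within about 8%, which could fairly be called in line. The planned sample also follows from the main production power analysis (n=120), not from the .93. All of this stands, and it limits the weight of the point. It does not rescue the lab-recast mean, which zero-mean scoring noise cannot move, or the equal gains in the two lab arms. Home recasts also stays clearly short on SD.

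Two stronger readings are not supported.

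- **True power is .80 to .86.** A reader might add independent noise until the home SDs reach 4.0 and substitute the power that results. That would drop the pre-post correlation to 2.15/4.0 = .54 and raise the change SD to √(4.0² − 2.15²) = 3.37, against the .90 and 2.06 of Aim 1. It repairs one input by breaking another.
- **Table 1's lab quartiles contradict the attendance text.** A reader might infer that half the children with perfect attendance forces a median of 960. With an exact half-and-half split, the median falls on the group boundary. If the best non-perfect attender has 15 sessions (900), the usual median is (900 + 960)/2 = 930, and 912 also lies between 900 and 960. The first quartile is also on a boundary, and 768 lies between 12 sessions (720) and 13 (780). No contradiction is shown.

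**Conclusion.** The point holds in a limited form. On the printed inputs the reported check is not met: the lab-recast mean is about 2.3 points low and out of reach, the lab arms do not differ where Aim 1 puts them 2 points apart, and the SDs are too small as described. After the adjustments most favourable to the plan, the lab means still fail and the home-recast SD is about 16% short.

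A reader might infer that the check was never made. The documents do not show that. An unstated noise term or a different gain rule may have been used, but the section says it is making its method clear and describes neither.

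Power fell in nearly every variant when variance was added, so the direction is supported. The size is not, because it depends on how the missing variance relates to pretest. The ranges rest on uniform dose within quartile bands and on a change-score approximation.

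**What to change.** 1. Recalibrate the simulated gain per exposure and the residual variation, or state any extra noise term already used, so that each arm reproduces its Aim 1 mean, SD and .90 pre-post correlation.
2. Report the achieved mean and SD by arm beside the Aim 1 values.
3. Rerun the existing code and restate the .93, naming the fitted model (dose with time alone, or with treatment) and the sample (two home arms or all 120 children).

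If the simulation is not rerun, withdraw the statement that the check was met and present the .93 as conditional on the generator described, without a substitute figure. Table 1's lab quartiles need no change on this account.

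The cost is one rerun and a few sentences. Design, sample size and conduct are untouched, and the stated power may become less favourable.
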